7.3 Trial participant exclusion criteria

1. Females who are pregnant, planning pregnancy or breastfeeding
2. Women of child-bearing potential and males with partners of child bearing potential who do not practice an acceptable method of birth control [acceptable methods of birth control in this study are: surgical sterilization, intrauterine devices, oral contraceptive, contraceptive patch, long-acting injectable contraceptive, partner's vasectomy, a double-protection method (condom or diaphragm with spermicide), total abstinence from intercourse with male partners. Abstinence is acceptable only as true abstinence: when this is in line with the preferred and usual lifestyle of the patient. Periodic abstinence (e.g., calendar, ovulation, symptothermal, post-ovulation methods), occasional abstinence and withdrawal are not acceptable methods of contraception.]
3. Subjects who meet any of the following criteria which tend to suggest advanced disease:
 - A) Speech impairment as assessed by a score of ≥ 3 on UMSARS question 1
 - B) Swallowing impairment as assessed by a score of ≥ 3 on UMSARS question 2
 - C) Impairment in ambulation as assessed by a score of >3 on UMSARS question 7
 - D) Falling more frequently than once per week as assessed by a score of ≥ 3 on UMSARS question 8
4. Participants with a clinically significant or unstable medical or surgical condition that, in the opinion of the investigator, might preclude safe completion of the study.
5. Participants with active malignant neoplasms or history of malignant neoplasm in the last 5 years.
6. Movement disorders other than MSA; e.g., Parkinson disease, dementia with Lewy bodies, essential tremor, progressive supranuclear palsy, spinocerebellar ataxia, spastic paraparesis, corticobasal degeneration, or vascular, pharmacological or post-encephalitic parkinsonism.
7. Concurrent dementia defined by a score lower than 21 on the MoCA.
8. Concurrent severe depression defined by a score ≥ 30 on the Beck Depression Inventory-II

9. History of deep brain stimulation surgery.
10. Patients with Body mass index <18.5.
11. Currently active infection that cannot be stabilised before baseline visit.
12. Patients with Diabetes (glycated haemoglobin [HbA1c] ≥ 48mmol/l at screening or random blood glucose >11.1 mmol/L)
13. End stage renal disease or severely impaired renal function with creatinine clearance <30ml/min
14. History of severe cardiac disease (Angina, Myocardial infarction or cardiac surgery in preceding 2 years)
15. History of pancreatitis
16. History of alcoholism
 1. Severe gastrointestinal disease including gastroparesis
 2. Ongoing treatment with sulphonylurea
 3. Concurrent and/or recent involvement in other research or use of another experimental investigational medicinal product within 90 days of study enrolment
 4. Known allergies to the IMP and excipients of IMP.

7.4 Recruitment

Initial discussions with patients at scientific and patient support meetings show very high interest in this study. A cohort of patients at the National Hospital for Neurology and Neurosurgery and patients will be utilised for recruitment as well as working with hospitals from surrounding areas. Neurologists in the UK with an interest in MSA will be informed when the trial is open to recruitment and provided with details of eligibility criteria to allow referral of potential recruits to the clinical trial team.

The REC approved “lay summary of the trial” will be provided to the MSA Trust website managers, the UCL Institute of Neurology, UCLH NHS Trust and local National Institute of Health Research Clinical Research Network portfolio websites. Contact details of the trial team will be included to allow potentially eligible interest patients to make direct enquires to the trial team.

All participants will be pre-screened by recognised experts in Movement Disorders to avoid any variability in diagnoses; using the history of their symptoms, supported by all available clinical correspondence according to usual standard of care.

It is anticipated that recruitment of 50 patients will be completed within 15 months of trial commencement.

Participant recruitment at a site will only commence when the trial has

1. Been initiated by the Sponsor (or it's delegated representative), and
2. Issued with the ‘Open to Recruitment’ letter.

Patients will be recruited from the National Hospital for Neurology & Neurosurgery, London. Patients attending their routine follow up appointments will be informed about the trial by their Neurologist and given a Patient Information Sheet, either by hand, by post or via email. This will

be documented in the medical records. Each potential patient will be pre-screened according to those inclusion/exclusion criteria which can be assessed ahead of obtaining informed consent. At the individual's request, their contact details will be passed to the trial Investigator.

7.5 Informed consent procedure

It is the responsibility of the Investigator, or a person delegated by the Investigator to obtain written informed consent from each participant prior to participation in the trial, following adequate explanation of the aims, methods, anticipated benefits and potential hazards of the trial.

The person taking consent will be GCP trained, suitably qualified and experienced, and will have been delegated this duty by the CI/ PI on the Staff Signature and Delegation of Tasks.

“Adequate time” must be given for consideration by the participant before taking part. Consent will be sought at least 24 hours after being given the study documentation. It must be recorded in the participant's notes in the electronic health record system, EPIC, when the participant information sheet (PIS) has been given to the participant.

The Investigator or designee will explain that participants are under no obligation to enter the trial and that they can withdraw at any time during the trial, without having to give a reason. During the consent process it will be highlighted to the participant by the investigator that they will have a 50% chance of being allocated to randomly to active Exenatide treatment or as a control.

No clinical trial procedures will be conducted prior to the participant giving consent by signing the Consent form. Consent will not denote enrolment into trial. Participants who are unable to write (eg due to severe tremor) will be able to indicate their informed consent verbally and a witness will sign the consent form on their behalf.

A copy of the signed informed consent form will be given to the participant. The original signed form will be retained in the trial file at site and a copy placed in the medical notes.

The PIS and consent form will be reviewed and updated if necessary throughout the trial (e.g. where new safety information becomes available) and participants will be re-consented as appropriate.

8 Trial procedures

The trial includes a screening visit (Visit 1), a baseline visit (Visit 2), a 12 week follow up (Visit 3), a 24-week follow-up visit (Visit 4), a 36 week follow up (Visit 5), 48-week follow-up visit (Visit 6), a 58-week telephone review and a final 96-week follow-up visit (Visit 7).

8.1 Pre-treatment Assessments

Screening assessments – Visit 1

Short title: Exenatide once-weekly as a treatment for Multiple System Atrophy Sponsor code: 125591

Participants will attend the research centre for informed consent to the trial. The following trial specific procedures will be carried out after consent to assess the participant's eligibility:

- Demographics recorded
- Medical History recorded
- Family History recorded
- All available brain imaging will be recorded
- Any previous genetic tests recorded e.g. if testing has been performed for Spinocerebellar ataxia or Fragile X tremor/ataxia syndrome
- Previous drug compliance issues recorded
- Physical Examination
- Neurological Examination
- 12-Lead ECG
- Routine bloods (FBC, U&E, LFT, glucose, amylase, HbA1c, PT and APTT)
- Height and weight
- Vital signs
- Serum and urine pregnancy test (for women of child bearing potential)
- MoCA
- BDI-II
- Concomitant Medications

At this visit the investigator will also ensure the patient is asked about speech/swallowing and mobility to assess exclusion criteria number 3. Eligible patients will wear a sensor attached by sticking plaster over their lower back for 1 week. They will bring this back to the trial team at the baseline visit or send to the trial team using a Stamped Addressed Envelope.

Participants will be randomised to either the trial drug or control arm.

Week 0 (Baseline assessments) – Visit 2

Patients will attend the research centre for the following trial procedures:

- Physical Examination (if deemed necessary by trial clinician for clinical purposes)
- Neurological Examination (if deemed necessary by trial clinician for clinical purposes)
- Lumbar puncture for CSF collection
- Serum collection
- Fasting blood tests (glucose, insulin, c-peptide and triglycerides)
- Vital signs
- UMSARS
- COMPASS Select
- MSA-QoL scale
- Timed Motor Tests
- The Unified Dystonia Rating scale
- MoCA
- BDI-II

- Concomitant Medications review
- Adverse Events review

Participants randomised to the trial drug arm will be dispensed the trial medication and receive teaching on its use.

All pre-treatment procedures will be carried out as specified in the schedule of assessments (appendix 1).

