6.6 Post-trial IMP arrangements

The IMP will not be provided to trial participants' post-trial participation.

7 Selection of Participants

The investigator should only enrol subjects who meet all inclusion and none of the exclusion criteria, are not put at undue risk by participating in the trial and can be expected to comply with the protocol.

There will be NO EXCEPTIONS to eligibility requirements at the time of randomisation. Previous clinical correspondence will be used to confirm eligibility criteria. Questions about eligibility criteria should be addressed PRIOR to attempting to randomise the participant.

The eligibility criteria for this trial have been carefully considered and are the standards used to ensure that only medically appropriate participants are entered. Participants not meeting the criteria should not be entered into the trial for their safety and to ensure that the trial results can be appropriately used to make future treatment decisions for other people with similar diseases or conditions. It is therefore vital that exceptions are not made to these eligibility criteria.

Participants will be considered eligible for enrolment in this trial if they fulfil all the inclusion criteria and none of the exclusion criteria as defined below.

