Appendix 1 - Schedule of assessments

1. Medical History: including MSA history, family history, medication history, previous imaging, previous genetic tests and previous drug compliance issues.
2. Vital signs: blood pressure, respiratory rate, heart rate, temperature, oxygen saturation and weight.
3. Routine blood tests: FBC, U&E, LFT, glucose, amylase, HbA1c, PT and APTT (PT and APTT not done at weeks 24 and 36).
4. Fasting blood tests
 - Baseline visit: glucose, insulin, c-peptide, and triglycerides.
 - Week 24 visit: glucose, insulin, c-peptide.
 - Week 48 visit: glucose, insulin, c-peptide.
5. 5 IMP administration: Participants will be randomly allocated into 2 groups to receive either Exenatide (n[~]=25) or best medical treatment (n[~]=25). Only participants randomised to the Exenatide arm will receive the IMP.
 6. At Week 4 the study nurse will call the participants to provide support and optimise compliance.
 7. At Week 58 the study nurse will call the participants to perform an adverse event check.

8. Randomisation will occur once eligibility has been confirmed prior to Visit 2 to allow Pharmacy team time to prepare IMP for dispensing.
9. * Clinical and Neurological examinations will be performed with deemed relevant/necessary by trial clinician for clinical purposes.
10. Only a serum sample will be collected for research purposes at week 96.

Appendix 2

COVID19 mitigation plans

The objective of this Appendix is to set out a plan detailing the proposed continuation of the Exenatide-MSA trial if a restriction in trial Face to Face visits should occur as a result of a resurgence of COVID19 infections.

CONTINUATION OF IMP DISPENSING FOR EXISTING TRIAL RECRUITS

1. Patient consent required. Each patient will be contacted by the research team, at site. Consent to ship IMP to the patients home to be fully documented in source notes
2. Patient will be assessed via telephone by Chief Investigator (or appropriate delegated trial team member) to decipher whether suitable to dispense IMP. Specific questions to be asked in relation to abdominal pain/ weight/ AEs/ new con-meds etc.

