#### 7.1.2 Secondary outcomes

- Patients with loss of independent ambulation by the end of the study, defined by a score of 4 in UMSARS-I item 7 (walking);
- Multiple System Atrophy health-related Quality of life (MSA-QoL) scale at week 48;
- UMSARS score (Parts III and IV) at week 48;
- Anti-parkinsonian or anti-orthostatic hypotension drugs comparing exenatide at week 48;
- The number of falls at week 48;
- Patients reaching a score of 3 or more on UMSARS-I items 1 (speech), 2 (swallowing), and 8 (falling) at week 48;
- Clinical global impression (CGI) at week 48;
- Montreal Cognitive Assessment (MoCA) scores at week 48;
- Safety of exenatide in MSA based on Adverse event reporting.

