### 7.1.4 Timing of outcomes

Table 1 provides an overview of primary and secondary outcomes and the time points at which they will be collected.

Table 1: Data collection measures and time points.

| Measure                      | 0 | 4* | 12 | 24 | 36 | 48 | 58* | 96 |
|------------------------------|---|----|----|----|----|----|-----|----|
| Screening measures           |   |    |    |    |    |    |     |    |
| Physical Examination         | ✓ |    | ✓  | ✓  | ✓  | ✓  |     | ✓  |
| Neurological Examination     | ✓ |    |    | ✓  |    | ✓  |     | ✓  |
| Vital Signs including weight | ✓ |    | ✓  | ✓  | ✓  | ✓  |     | ✓  |
| Fasting blood test           | ✓ |    |    | ✓  |    | ✓  |     |    |
| Eligibility confirmation     | ✓ |    |    |    |    |    |     |    |
| Primary outcome              |   |    |    |    |    |    |     |    |
| UMSARS Part 1, 3 and 4       | ✓ |    | ✓  | ✓  | ✓  | ✓  |     | ✓  |
| UMSARS Part 2                | ✓ |    | ✓  | ✓  | ✓  | ✓  |     | ✓  |
| Secondary outcomes           |   |    |    |    |    |    |     |    |
| MSA-QoL scale                | ✓ |    |    |    |    | ✓  |     | ✓  |
| MoCA                         | ✓ |    | ✓  | ✓  | ✓  | ✓  |     | ✓  |
| Serum collection             | ✓ |    | ✓  | ✓  | ✓  | ✓  |     | ✓  |
| CSF collection               | ✓ |    |    |    |    | ✓  |     |    |
| Other measures               |   |    |    |    |    |    |     |    |
| BDI-II                       | ✓ |    | ✓  | ✓  | ✓  | ✓  |     | ✓  |
| COMPASS Select               | ✓ |    |    | ✓  |    | ✓  |     | ✓  |
| COMPASS Change               |   |    |    | ✓  |    | ✓  |     | ✓  |
| Timed Motor Tests            | ✓ |    |    | ✓  |    | ✓  |     | ✓  |
| The Unified Dystonia Rating  | ✓ |    | ✓  | ✓  | ✓  | ✓  |     | ✓  |
| IMP administration           | ✓ |    |    | ✓  | ✓  | ✓  |     |    |
| Adverse Events/SAEs review   | ✓ | ✓  | ✓  | ✓  | ✓  | ✓  | ✓   |    |
| Concomitant Medication       | ✓ | ✓  | ✓  | ✓  | ✓  | ✓  |     |    |

\*: Telephone call

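### Exclusion criterion 3 is set by UMSARS item scores that screening does not schedule, and the milestone analyses do not set aside patients already at the same cut-offs

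*Protocol*

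**What the plan says.** **Eligibility.** Each limb of criterion 3 in Protocol 7.3 is a UMSARS item score. For speech it is "Speech impairment as assessed by a score of ≥ 3 on UMSARS question 1", for swallowing "Swallowing impairment as assessed by a score of ≥ 3 on UMSARS question 2", and for falls "Falling more frequently than once per week as assessed by a score of ≥ 3 on UMSARS question 8". The walking limb excludes a score above 3 on item 7. Protocol section 7 adds: "There will be NO EXCEPTIONS to eligibility requirements at the time of randomisation".

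**Screening.** The Visit 1 list in Protocol 8.1 includes MoCA and BDI-II but not UMSARS, which first appears in the Week 0 (Visit 2) list. For criterion 3 the Visit 1 text says: "At this visit the investigator will also ensure the patient is asked about speech/swallowing and mobility to assess exclusion criteria number 3".

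**Timing of allocation.** Protocol 8.1 mentions randomisation at the end of the Visit 1 text. Appendix 1 footnote 8 states: "Randomisation will occur once eligibility has been confirmed prior to Visit 2 to allow Pharmacy team time to prepare IMP for dispensing". Protocol 11.3 instead has the investigator enter the patient into the randomisation system at the baseline visit.

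**Outcomes.** SAP 7.1.2 lists "Patients reaching a score of 3 or more on UMSARS-I items 1 (speech), 2 (swallowing), and 8 (falling) at week 48", and also loss of independent ambulation, defined as a score of 4 on item 7. SAP 7.1.3 repeats the speech, swallowing and falling milestones at week 96.

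**Models.** SAP 7.3 uses logistic regression for binary outcomes, adjusted for MSA subtype. Baseline adjustment is specified for numerical outcomes only. SAP 7.4 applies the same models to the exploratory outcomes.

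**The concern.** Because the entry criterion and the milestones share their cut-offs, the criterion is what makes each milestone a new event. Apply it reliably before allocation, and every patient starts below every threshold, so week 48 status equals progression. If it rests on unscored questioning, some patients may enter at or above a threshold, and the SAP has no second safeguard. A patient scoring 3 on item 1 both at baseline and at week 48 would count as having reached 3, although nothing changed.

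The other two exclusions defined by a rating scale, dementia by MoCA and depression by BDI-II, both have their instrument on the Visit 1 list. Criterion 3 is the exception, which looks more like an omission than a choice. Neither document says what to do if the first scheduled UMSARS shows that a randomised patient breaches criterion 3.

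**Working it through.** **1. The plan's own figures.** The denominators come from the sample size section. The residual SD is 10.4 × √(1 − 0.85²) = 5.48. For a 5-point difference, 20 per arm gives 80.2% power by a t-based calculation, and 40/(1 − 0.20) = 50, or 25 per arm. The plan's figures reproduce. The point does not depend on them beyond the arm sizes of 25 (randomised) and 20 (after dropout).

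**2. Cut-offs side by side.**

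| Item | Exclusion (Protocol 7.3) | Milestone (SAP 7.1.2) | Named in Visit 1 prompt |
|---|---|---|---|
| 1 speech | 3 or more | 3 or more | yes |
| 2 swallowing | 3 or more | 3 or more | yes |
| 7 walking | above 3, i.e. 4 | 4 | as mobility |
| 8 falling | 3 or more | 3 or more | no |

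Items run from 0 to 4 (SAP 9.1), so above 3 means 4. All four pairs coincide.

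**3. Order of events.**
- Protocol 8.1 and Appendix 1 footnote 8: Visit 1, then randomisation, then Visit 2 with the first listed UMSARS.
- Protocol 11.3: randomisation at the baseline visit, with no statement that UMSARS is scored first.
- Protocol 8.2: randomisation after eligibility is confirmed, pointing to the 8.1 assessments. Section 8.1 covers both Visit 1 and Visit 2, so this does not settle the order.

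None of these texts requires a recorded UMSARS item score before allocation.

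**4. Effect of one patient already at a cut-off.** The arm's proportion rises by 1/25 = 4 points, or 1/20 = 5 points. Two in one arm add 8 to 10 points.

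**5. Dilution (assumed inputs).** Let a share q of each arm be at the cut-off from the start and remain there. The observed proportion is q + (1 − q)p, so the observed difference is (1 − q) times the true one. Assume new-event rates of 40% and 20%. At q = 10%, the proportions are 0.10 + 0.90 × 0.40 = 0.46 and 0.10 + 0.90 × 0.20 = 0.28, a difference of 0.18. Power is for a two-sided 5% normal-approximation test of two proportions, 25 per arm.

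| q | Observed difference (points) | Power |
|---|---|---|
| 0 | 20.0 | 0.335 |
| 4% | 19.2 | 0.300 |
| 10% | 18.0 | 0.257 |
| 20% | 16.0 | 0.203 |

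**6. Chance imbalance (assumed count).** Suppose 5 of 50 patients start at a cut-off and are split at random 25/25. The number in one arm is hypergeometric.
- P(5:0 or 0:5) = 2 × C(25,5)/C(50,5) = 2 × 53,130/2,118,760 = 0.050.
- P(4:1 or 1:4) = 2 × 25 × C(25,4)/C(50,5) = 2 × 25 × 12,650/2,118,760 = 0.299.

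Together this is 0.349, a 35% chance of a gap of at least 3 patients, or 3/25 = 12 points, unrelated to treatment.

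**The case against.** The opposing case has real force, and several stronger readings fail against it.

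- **That falls are never asked about.** A reader might infer this, but the prompt serves criterion 3 as a whole and mobility may be taken to include falls. The documents support only that falling is not named.
- **That no score is obtained at screening.** Criterion 3 is worded as a score, and SAP 9.1 describes Part I as a historical review, so an investigator could score it by interview. Expert pre-screening and clinical correspondence (Protocol 7.4 and section 7) also help. What stands is that no text schedules or records the score.
- **That the deciding scores always follow allocation.** Protocol 8.1 and footnote 8 imply this, but Protocol 11.3 does not. It is a conflict to reconcile, not an established sequence.
- **That SAP Table 1 shows eligibility being decided after allocation.** Its "Eligibility confirmation" row is marked at week 0, but the table has no screening column, so the mark says nothing about order. The Appendix 1 grid has lost its column alignment in the text available and cannot settle whether UMSARS is marked at screening.
- **That ineligible patients would be dropped selectively by arm.** SAP 5.3 keeps all randomised patients, apart from those who withdraw and also withdraw permission to use their data.

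The impact is also bounded. Patients at a cut-off before randomisation are balanced in expectation, so the arms remain comparable on week 48 status. The cost is dilution, chance imbalance and an outcome that no longer means progression. Protocol 11.4.3 does call for baseline adjustment where feasible, but SAP 7.3 does not carry this through to binary outcomes.

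**Conclusion.** The point holds as a low-cost improvement. A score-based exclusion has no scheduled score at screening, the prompt leaves one of four limbs unnamed, the randomisation time is stated inconsistently, and the SAP would count a patient already at a cut-off, and still there at week 48, as an event. The size is 4 to 5 percentage points of an arm's proportion per patient. The documents do not give the number of such patients, and it could be zero; the dilution and imbalance figures rest on assumed rates and counts.

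A reader might take this as a threat to the main result. The documents do not support that: the primary model in SAP 7.2 adjusts for baseline UMSARS, and SAP 7.3 describes the secondary and other analyses as supportive.

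**What to change.** 1. **Protocol 8.1:** add to Visit 1 that UMSARS-I items 1, 2, 7 and 8 are scored, entered in the CRF before randomisation, and used to decide criterion 3. Name falling in the prompt.
2. **Protocol 8.1, 11.3 and Appendix 1 footnote 8:** reconcile these to one randomisation time that follows the scoring.
3. **SAP 7.1.2, 7.1.3 and 7.3:** count a milestone only in patients below the cut-off on the pre-randomisation item score, or add that item score to the logistic model. For patients already enrolled, use the Visit 2 score and state that it may have been rated with the arm known.

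The cost is four interview items at a visit that already covers most of these topics, and short text changes in each document. If the restriction is chosen, slightly fewer patients enter the milestone analyses; adjustment keeps them all. If enrolment has closed, the SAP change can still be made before analysis.
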